### 1.3 Objective

This is a feasibility trial, examining whether it is possible to run a full multicentre randomised controlled trial of the following hypothesis; In patients undergoing repair of neck of femur fracture, does the use of continuous non-invasive blood pressure monitoring compared to intermittent non-

invasive blood pressure monitoring improve intraoperative haemodynamic stability and post-operative outcomes.

#### **1.4 Need for a trial**

There is a strong body of evidence demonstrating that patients who experience intraoperative hypotension are at higher risk of death and adverse post-operative outcomes. There is evidence that intermittent non-invasive blood pressure may be inadequate for detecting intraoperative hypotension. There is a lack of high quality evidence examining whether using continuous non-invasive blood pressure monitoring can improve the intra-operative haemodynamic stability by detecting hypotension more effectively and whether doing so leads to a reduction in adverse post-operative outcomes. As the incidence of intra-operative hypotension, and adverse post-operative outcomes is high in patients undergoing repair of fractured neck of femur, this group of patients has a high propensity to benefit from such an intervention if the hypothesis is proved true, and therefore present an ideal study cohort.

#### **1.5 Ethical considerations**

The trial will be conducted in full conformance with the principles of the Declaration of Helsinki and to Good Clinical Practice (GCP) guidelines. It will also comply with all applicable UK legislation. All data will be stored securely and held in accordance with Data Protection Act 2018 and the General Data Protection Regulation (2018)

#### **1.6 CONSORT**

The trial will be reported in line with the CONSORT (Consolidated Standards of Reporting Trials) statement (Lancet 2001, **357**: 1191-1194).

[figure not shown]
## **2. TRIAL DESIGN**

### **2.1 Trial summary and flow diagram**

This is a feasibility 'before and after' controlled trial, investigating whether it is feasible to conduct a trial testing the hypothesis that the use of continuous non-invasive blood pressure monitoring improves intraoperative haemodynamic stability in patients undergoing repair of fractured neck of femur. The primary endpoint is the proportion of eligible patients who complete the study protocol. Secondary endpoints will include analysis of the effectiveness of patient identification, the reasons for exclusions or failure to complete the study protocol, and an analysis of the incidence of the primary and secondary outcomes planned for the definitive study.

**Figure 1** Trial flow diagram

**Connection to CNAP monitor (the intervention)**

[figure not shown]
All patients included in the trial will have CNAP monitoring. The first cohort of patients (before) will have CNAP monitoring but the monitoring readings will not be visible to the

treating anaesthetist. The second cohort ('after') will have CNAP monitoring connected and visible for clinical use by the treating anaesthetist. In each case, normal clinical monitoring will be applied (non-invasive intermittent blood pressure monitoring). The systems will be applied on opposite arms, allowing the CNAP monitor to use its own automatic calibration without disturbing the standard monitoring.

The 'Standard monitoring' NIBP cuff will inflate approximately every 3-5 minutes, whereas the CNAP calibration cuff will only inflate every 20-30. As such we will recommend that the CNAP cuff is placed on the same arm as IV access is established, to offer the lowest chance of impeding flow of IV medication. However, this will not be mandatory, and ultimately it is up to the treating anaesthetist to determine the best position for IV access. Where there is an interruption in CNAP use because of IV access, the patient will be excluded from the study. This will form part of the feasibility analysis.

Figure 1 – Arrangement of Standard and CNAP monitoring, including suggested positioning of intravenous access.

## 2.2 Aims and objectives

### 2.2.1 Primary objective

The primary objective of this trial is to evaluate whether it is feasible to undertake before and after controlled trial to test the effect of using continuous non-invasive blood pressure monitoring versus standard intermittent non-invasive blood pressure monitoring on intraoperative haemodynamic stability and post-operative outcomes.

### 2.2.2 Secondary objective

Secondary objectives of the trial are to

- Assess the effectiveness of patient identification and screening
- Assess the effectiveness of the blinding
- Identify reasons for failure to recruit patients and screen fails

▪ Explore barriers and facilitators to recruitment

▪ Evaluate the robustness and completeness of data collection.

- Identify the proportion of patients with complete follow up at 30 days
- Identify the incidence of haemodynamic instability by evaluating the nadir blood pressure, the absolute time spent below blood pressure thresholds, and the proportion of anaesthetic time spent with a blood pressure outside defined limits.
- Identify the frequency of occurrence of technical difficulties with the CNAP equipment.
- Identify the incidence of post operative acute kidney injury, myocardial injury, stroke, and death in the post-operative period.

### 2.2.3 Measures of success

The success of this feasibility trial will be assessed by the trial management group, to consider whether we should apply for funding for a larger, definitive trial. The assessment will be based on the data generated from this feasibility study, and key parameters for assessment will include:

- What is the rate of recruitment
- What is the effectiveness of the process for identifying and screening patients, and what are the reasons for failure to recruit patients if/when this occurs. This will include analysis of reasons patients give for declining consent (if given).
- Are clinicians willing to recruit patients into the study
- Was the CNAP equipment reliable and easy to use?
- Can the CNAP equipment be started by research team and left unattended without any intervention?
- Are the data collection processes during the hospital stay adequate? How complete is the data for the important perioperative parameters?
- What is the rate of follow up of patients at 30 days? What are the reasons for loss of follow-up if any?

## 2.3 Outcome measures

### 2.3.1 Feasibility Outcomes

- Proportion of eligible patients recruited
- Proportion of recruited patients in whom CNAP was successfully applied and full data collected.
- Proportion of patients with complete in-hospital data set
- Proportion of patients with complete follow up data.

### 2.3.2 Intraoperative Outcomes

- Nadir blood pressure; the lowest recorded mean arterial pressure, as per CNAP recording (blinded or otherwise)

- Absolute intra-operative time spent with mean arterial pressure <55mmHg, <65mmHg, <80mmHg.
- Total dose of fluid given intra-operatively
- Total dose of vasopressors given intra-operatively.

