## Description of CNAP

Continuous non-invasive blood pressure (cNIBP) monitoring is available from a number of manufacturers, marketed under the names CNAP by CNSystems, ClearSight from Edwards Life Sciences, Finapres from Finapres Systems to name three. These systems work by applying the Penaz Principle; if arterial blood flow into a finger can be detected by photoplethysmography the pressure required in a cuff around the finger to arrest blood flow will be proportional to the pressure driving blood into the finger; the arterial pressure. cNIBP can be measured using this principle with systems calibrated by more traditional upper-arm oscillometrically derived measurements.

There have been a number of observational studies examining whether cNIBP is equivalent or inferior to continuous *invasive* blood pressure monitoring (iABP), in terms of accuracy (or bias; the difference between the measured value, in this case with cNIBP and the reference value, in this case with iABP), and precision (the extent to which the measured value varies due to random error). Additionally, the ability to reflect changes in arterial blood pressure in a timely, or real-time fashion have been evaluated.

Kim et al [15] included a number of photoplethysmographical devices as well as the 'T-Line' tonometry in a systematic review of continuous non-invasive blood pressure measurement systems. They found that in 7 studies using CNAP, when compared to invasive intra-arterial blood pressure monitoring, the bias for systolic arterial pressure was  $-1.8 \pm 12.8$  (95% LOA: -26.8 to 23.2 mmHg), the bias for diastolic blood pressure was  $7.2 \pm 8.5$  (-9.5 to 24.0 mmHg) and the bias for mean arterial pressure was  $5.5 \pm 9.3$  (-12.7 to 23.6 mmHg).

There are far fewer studies comparing cNIBP systems to conventional intermittent oscillometric blood pressure measurement. Chen et al., [16] compared non-invasive blood pressure measurements made using an intermittent cuff and the Nexfin device in 25 patients undergoing supine abdominal or orthopaedic surgery, and found an overall bias in measurements of systolic blood pressure of  $-1 \pm 12$  mmHg. Importantly, they found that the trending ability of the cNIBP system was at least equivalent to that of the intermittent cuff device.

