Juri et al., [17] performed Bland-Altman analysis in 20 patients undergoing elective knee arthroplasty found a MAP bias of  $-1.8 \pm 8.1$  mmHg when comparing the ClearSight device to intermittent cuff measurements of MAP during the intra-operative period. However, during induction of anaesthesia they found a mean bias in MAP of  $-8.7 \pm 14.4$  mmHg with 95% limit of agreement of 28.3 mmHg, giving an overall MAP bias of  $-3.9 \pm 10.3$  mmHg with 20.5 mmHg 95% limit of agreement.

Balzer et al., [18] found that the bias in blood pressure measurements by the Nexfin cNIBP device compared to invasively measurement blood pressure was smaller than that of intermittent oscillometrically measured blood pressure compared to the same (MAP; Nexfin  $-1 \pm 13$ , Intermittent cuff  $13 \pm 13$ , mmHg, percentage error 27 vs 30%).

Although cNIBP measurement appears to be slower at detecting hypotension (see [19]; the lowest systolic blood pressure was detected 10.5 seconds slower by cNIBP than by iABP), it is significantly quicker than by an intermittent oscillometrically obtained measurement, which takes 30-60 seconds to complete, and in many cases is only performed every 3-5 minutes. As such, although based on current evidence, and supported by Kim's systematic review and meta-analysis, cNIBP cannot yet replace invasive blood pressure monitoring in those who need it, it offers significant advantages over intermittent non-invasive blood pressure monitoring which are worth exploring.

A number of trials have supported the view that cNIBP monitoring is superior to intermittent NIBP monitoring. Illies and colleagues studied connected CNAP monitoring to 65 pregnant women iStabilise Protocol – IRAS 261698

undergoing elective caesarean section, but blinded the treating anaesthetist to the values recorded. They found that hypotension was detected in 55% of patients using traditional intermittent non-invasive blood pressure measurement, was detected in 91% of patients using CNAP continuous monitoring [20]. Additionally, Wagner and colleagues connected continuous non-invasive blood pressure monitoring to 130 patients in the emergency department resuscitation area, and found that 46 patients had episodes of hypotension with either systolic pressure <90mmHg or mean arterial pressure <65mmHg for >4 minutes that was *not* detected by the standard monitoring, and thus the clinical team was unaware of [21].

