### **2.9.3 Measures common to the intervention and control groups**

The vast majority of the perioperative care provided to the control and intervention groups will be similar. Pre-operative care will be unaltered. Once group allocation has occurred, there will be no restrictions on choice of anaesthetic technique (for example, choice of general or regional anaesthesia, choice of drugs).

Management of the patient’s blood pressure will be at the sole discretion of the anaesthetic team treating the patient. Baseline blood pressure (systolic, mean, and diastolic) will be calculated as the average of 2 readings 5 minutes apart before administration of any anaesthetic drugs. Both control and intervention groups will have ‘standard non-invasive blood pressure monitoring’ regardless of the availability of CNAP to the treating anaesthetist, as shown in the trial diagram. The frequency of readings will be chosen by the treating anaesthetist

Continuous non-invasive blood pressure monitoring will continue until the patient moves to the PACU.

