#### **5.1.1 Haemodynamic monitoring data**

Lidco CNAP recordings will be stored on the secure trust-based file system. Analysis will be performed using 'Lidcoview SE' software.

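### CNAP guides treatment in one cohort and appears to score hypotension in both, so its persistent error does not cancel from the comparison of time below 55 and 65 mmHg

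*Combined protocol and SAP*

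**What the plan says.** Every patient wears CNAP as well as a standard arm cuff (section 2.1.1). The first cohort "will have CNAP monitoring but the monitoring readings will not be visible to the" treating anaesthetist. The second "will have CNAP monitoring connected and visible for clinical use by the treating anaesthetist". Blood pressure management "will be at the sole discretion of the anaesthetic team treating the patient" (section 2.9.3), so treatment will follow whichever reading is in view.

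For the outcomes, section 2.3.2 defines nadir pressure as "the lowest recorded mean arterial pressure, as per CNAP recording (blinded or otherwise". The next item, "Absolute intra-operative time spent with mean arterial pressure <55mmHg, <65mmHg, <80mmHg", names no device, and neither does the matching item in section 6.1. That it also comes from CNAP is an inference from two places. Section 5.1.1 says "Lidco CNAP recordings will be stored on the secure trust-based file system" and names no other haemodynamic source for analysis. The rules for gaps in recording in section 2.9.4 are written for CNAP. No outcome is defined on the standard cuff. Nor is there an independent reference, because patients judged to need invasive monitoring are excluded (sections 2.4.2 and 2.9.4).

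Section 2.1 says the study will look at the incidence of the outcomes planned for the definitive study. Section 2.2.2 makes the incidence of instability a secondary objective. Section 6.1 says the data, with the literature, will be used to size a full trial.

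**The concern.** Using one device in both cohorts looks like a safeguard: whatever error CNAP has should enter both records alike and drop out of the comparison. That needs the error to be handled alike in both cohorts, and here it is not. If CNAP reads persistently low in an intervention patient, the anaesthetist sees the low value and treats it, and the CNAP record returns to target. If it reads persistently low in a control patient, nobody sees it. The cuff is held at target and the CNAP record stays low. The control record is therefore more spread out than the intervention record even when true pressure is equally well controlled.

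A wider spread puts more recorded time below a threshold that lies well under the usual pressure, such as 55 or 65. The comparison could then show less hypotension with visible CNAP when patients' true exposure had not changed, and that estimate could enter the planning of the full trial.

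**Working it through.** **Plan's own figures.** The 30 patients come with no formula or inputs, and no between-cohort test is specified, so there is no calculation to reproduce. One check on the cited device data: for CNAP against invasive pressure the text beginning "the bias for mean arterial pressure was" gives 5.5 ± 9.3 mmHg. Then 5.5 ± 1.96 × 9.3 = -12.7 to 23.7, against the cited -12.7 to 23.6, which agrees to rounding.

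**Inputs from the protocol.** D, the SD of the difference between a finger-cuff device and an arm cuff, is 8.1 mmHg, reported "when comparing the ClearSight device to intermittent cuff measurements of MAP during the intra-operative period"; over the whole case it is 10.3. Both come from a different finger-cuff device. The protocol gives no CNAP-versus-cuff figure.

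**Assumptions.** Each team holds the pressure it steers by at mean T = 75, SD s = 8. Controls steer by the cuff and intervention by CNAP alone. The mean offset is zero. The two devices have equal, independent error (variance D²/2 each), so true pressure has the same distribution in both cohorts.

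**Formulas, all error persistent.**
- Control, CNAP record: Φ((threshold - T)/√(s² + D²)), with √(64 + 65.61) = 11.385
- Intervention, CNAP record: Φ((threshold - T)/s)
- True pressure, both cohorts: Φ((threshold - T)/√(s² + D²/2)), with √(64 + 32.805) = 9.839

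| MAP below | CNAP, control | CNAP, intervention | True, both |
|---|---|---|---|
| 55 | 3.9% | 0.6% | 2.1% |
| 65 | 19.0% | 10.6% | 15.5% |
| 80 | 67.0% | 73.4% | 69.4% |

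The order reverses at 80 because that threshold lies above the assumed mean. At T = 80 both records give 50%.

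**How much error persists (below 65).**
- Half the variance, SD 5.7, with the fast half left out of both records: Φ(-10/√(64 + 32.49)) = 15.4% in control v 10.6%.
- Half the variance, with fast CNAP noise kept in both records: Φ(-10/√(64 + 3 × 16.40)) = 17.4% v Φ(-10/√(64 + 16.40)) = 13.2%. The gap is 4 to 5 points either way.
- All fast noise: Φ(-10/√(64 + 32.805)) = 15.5% in both, so no artefact.

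**Other assumptions (below 65, all persistent, control v intervention).** T = 70: 33.0% v 26.6%. T = 80: 9.4% v 3.0%. s = 5: 14.7% v 2.3%. s = 10: 21.9% v 15.9%. D = 10.3: 22.2% v 10.6%.

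**Mean offset b = CNAP minus cuff, cuff unbiased on average (below 65).** Control CNAP becomes Φ((65 - T - b)/11.385), true intervention Φ((65 - T + b)/9.839), and cuff intervention Φ((65 - T + b)/11.385). Cuff control is Φ((65 - T)/8). Differences, intervention minus control, in percentage points:

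| b | CNAP | True | Cuff |
|---|---|---|---|
| -5.5 | -24.1 | -9.7 | -1.9 |
| 0 | -8.4 | 0.0 | +8.4 |
| +5.5 | +1.9 | +16.9 | +24.1 |

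In each row the CNAP contrast is more favourable to intervention than the truth, the cuff contrast is less favourable, and the two bracket it. The same holds below 55: at b = -5.5, 0 and +5.5 the CNAP contrast is -9.5, -3.3 and -0.6 against true differences of -1.6, 0.0 and +4.9.

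**Dilution.** In a simulated 90-minute case (D = 8.1, all persistent), steering by CNAP alone takes recorded time below 65 from 17.1 to 9.5 minutes while true time stays at 14.0. With half weight on CNAP and half on the cuff, recorded time goes from 17.1 to 12.0 and true time from 14.0 to 12.1. Of that 5.1-minute recorded fall, 1.9 minutes is real.

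**The case against.** Several points on the other side stand.

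- Only persistent error matters, and recalibration shrinks it. By how much cannot be settled from the text: section 2.1.1 has CNAP using its own automatic calibration on the opposite arm, while section 2.9.4 has a reading from the native monitoring calibrate it. These passages must be reconciled. Opposite-arm placement, with inter-arm MAP differences of up to 20 mmHg allowed by section 2.4.2, leaves room for a persistent part.
- Intervention anaesthetists see the cuff too, so steering by CNAP alone is an upper case.
- The 8.1 mmHg is another device's figure, and the sign of any CNAP-versus-cuff offset is unknown. At +5.5 the recorded contrast below 65 even leans slightly towards control. The bias relative to true pressure still favours intervention, so the unknown sign changes the recorded contrast but does not remove the bias.
- This is a 30-patient feasibility study. None of the measures of success in section 2.2.3 is a haemodynamic contrast.

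A reader might infer that any fall in recorded hypotension would be spurious. The documents do not support that: the artefact would add to any real effect of faster detection and says nothing about whether one exists. Nor is every threshold biased towards intervention, as the result at 80 shows.

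A reader might also infer that the cited 5.5 mmHg bias means incidence is understated and that raising the thresholds by 5.5 would correct it. With true MAP of mean 75 and SD 10, the shift alone turns 15.9% below 65 into Φ(-15.5/10) = 6.1%, but including the 9.3 mmHg SD gives Φ(-15.5/√(100 + 86.49)) = 12.8%. The protocol also does not spell out the order of subtraction. The shift is not a sound correction.

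**Conclusion.** The concern holds in limited form. CNAP guides treatment in one cohort and, on the natural reading, scores these outcomes in both, so its persistent error against the cuff does not cancel. With no true difference, the artefact below 65 mmHg runs from nothing (all fast noise) through 4 to 5 points (half persistent) to 8.4 points (all persistent) under the central assumptions. It also favours intervention below 55, and it can vanish or reverse below 80. The displayed mean and SD, the persistent share and the weight given to CNAP are assumptions, so these figures show plausible size and are not predictions. The feasibility outcomes are untouched. What is at risk is the CNAP-based contrast if it is used as an effect estimate for the full trial.

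**What to change.** In section 2.3.2, state that time below 55, 65 and 80 mmHg is taken from CNAP, if that is the intention. In both cohorts, also compute the lowest MAP and the time (or proportion of readings) below 55, 65 and 80 from the standard cuff readings that every patient already has. Report the two sets descriptively, side by side, as an approximate bracket. Add a sentence to section 6.1 that the CNAP-only contrast will not be carried forward as the effect estimate for the full trial. Reconcile the calibration descriptions in sections 2.1.1 and 2.9.4.

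The cost is a few lines of text and capture of charted cuff readings for 30 patients. The limits should be stated. Cuff readings are sparse, about every 3 to 5 minutes, and their frequency is chosen by the anaesthetist and may differ by cohort, so a cuff nadir is not directly comparable with a CNAP nadir. The bracket also depends on the model above. It should be read as a guide, and agreement between the two devices should not be made a condition for drawing conclusions.

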### **2.3.3 Post-Operative Outcomes**

- Outcomes as per standardised definitions from the European Perioperative Clinical Outcome standards [28].
- Incidence of acute kidney injury in the 7 days post-operatively
- Incidence of myocardial injury in the first 3 days after surgery (Troponin>0.03ng/ml judged to be due to myocardial injury)
- Stroke: Thrombotic, embolic or haemorrhagic where there is a persistent residual motor, sensory or cognitive dysfunction
- Surgical site infection (superficial or deep, as per CDC definitions – see [29])
- Mortality: in hospital, and at 30 days post-operatively

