**TRIAL SUMMARY**

Trial Title	Can continuous non-invasive monitoring improve stability of intraoperative blood pressure – A feasibility study in hip fracture surgery
ref. number	2019003AN
Clinical Phase	Phase III feasibility

Trial Design	Feasibility before-and-after trial	
Trial Participants	Adults undergoing surgery for repair of hip fracture	
Planned sample size	30 (15 control and 15 intervention patients)	
Treatment Duration	Intra-operative only.	
Follow-up Duration	In-hospital follow up to discharge, and mortality follow up to 30 days	
Planned Trial Period	From 01/06/2019-01/08/2019	
	Objectives	Outcome Measures
Primary	Demonstrate feasibility	Proportion of patients recruited who received the intervention, and completed follow up.
Secondary	Evaluate the incidence of intra-operative haemodynamic instability and post-operative adverse outcomes	Proportion of anaesthetic time with mean arterial pressure below set thresholds. Lowest recorded blood pressure. Amount of vasopressor and fluid given intraoperatively Post-operative incidence of acute kidney injury, myocardial infarction, stroke and death.

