#### *What is the incidence of adverse outcomes*

Abbot and colleagues [6] found that 2.8% of patients in the VISION study (Vascular events in non-cardiac surgery cohort evaluation) experienced myocardial injury (MINS; a transient post-operative rise in troponin levels which are associated with death [7]).

Maheshwari and colleagues found that in a retrospective study of 42,000 cases of non-cardiac surgery, 5% [95%CI 2-7%] of patients developed post-operative acute kidney injury [8]. O'Connor and colleagues [9] found that the acute kidney injury occurs in 10.9-16.4% of patients undergoing major abdominal surgery, and found this associated with a 12.6-fold [95% CI, 6.8-23.4] increase in the risk of death. Other studies have found similarly strong associations between post-operative acute kidney injury and death [10].

Estimates of the incidence of post-operative delirium vary depending on the population. Rudolph et al., (2009) found that delirium occurred in 8.5% of patients over 60 years of age undergoing non-cardiac surgery who did not have pre-existing neurocognitive dysfunction [11]. Bruce and colleagues found post-operative delirium occurred in 3-28.3% of patients undergoing elective orthopaedic surgery following a meta-analysis of 26 publications [12]. Hirsch and colleagues found that intra-operative hypotension was not associated with an increased risk of post-operative delirium, but the degree of intra-operative blood pressure fluctuation was [13].

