## **2.11 Concomitant illness and medication**

### **2.11.1 Concomitant illness**

Details of concomitant illness of relevance to the inclusion and exclusion criteria will be recorded. This will include presence of atrial fibrillation, peripheral vascular disease, scleroderma, an arteriovenous shunt, valvular heart disease. Details of concomitant illness of relevance to the analysis of the data will include known diagnosis of chronic arterial hypertension, chronic heart failure, ischaemic heart disease, chronic kidney disease, and diabetes mellitus.

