### 3.2 Laboratory assessments

There will be no laboratory assessments carried out specifically *by* the study. However, the study will record laboratory results of the serum creatinine concentration, serum troponin concentration, serum C-reactive Protein concentration, blood white cell count. These will be recorded from information available to the treating clinician only, and will not involve any research-specific samples.

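### Myocardial injury in section 2.3.3 has no pre-operative troponin comparator, so a level already raised before theatre can be counted as a new event

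*Combined protocol and SAP*

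**What the plan says.** All references are to the combined protocol and SAP.

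- **Outcome (section 2.3.3):** "Incidence of myocardial injury in the first 3 days after surgery (Troponin>0.03ng/ml judged to be due to myocardial injury". No pre-operative value, rise or repeat sample is mentioned. The first bullet of the same section adds "Outcomes as per standardised definitions from the European Perioperative Clinical Outcome standards [28", but the content of that reference is not reproduced.
- **Background (section 1.2, incidence of adverse outcomes):** the event is described as "a transient post-operative rise in troponin levels which are associated with death", and the cited incidence is "2.8% of patients in the VISION study".
- **Source of values (section 3.2):** "There will be no laboratory assessments carried out specifically" for the study. Of the results that are recorded, troponin among them, it says "These will be recorded from information available to the treating clinician only, and will not involve any research-specific samples". This is not limited to post-operative samples. Table 1 in section 3.1 schedules no baseline troponin.
- **Population:** section 2.11.1 records "chronic heart failure, ischaemic heart disease, chronic kidney disease, and diabetes mellitus" as relevant to the analysis. None of these is an exclusion in section 2.4.2.
- **Size and use:** the Trial Summary plans "30 (15 control and 15 intervention patients". Section 2.1 makes the incidence of the definitive study's planned outcomes a secondary endpoint. Section 6.1 says the feasibility data, together with the literature, will inform the definitive sample size. Section 6.1 and the Trial Summary name the cardiac outcome infarction, whereas sections 2.2.2 and 2.3.3 name it injury.

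**The concern.** The background describes a change that occurs after surgery, but the operational rule asks only for a level after surgery. The two agree only if the patient was below the cut-off beforehand, and nothing in the plan checks that. Conditions that could plausibly accompany a raised troponin before theatre are recorded but do not exclude a patient.

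At stake is what the reported incidence means. As written, it can mix injury that arose during or after the operation with elevation already present on arrival in theatre, which intra-operative blood pressure cannot have caused. Because the incidence is to be carried forward into planning, the feasibility study is the cheapest place to separate the two.

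**Working it through.** The plan derives no figure from this outcome, so there is no calculation of its own to reproduce. The 30 patients rest on judgement in section 6.1, and 15 + 15 = 30 agrees with the Trial Summary.

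**1. Following the rule as written.** Take a patient above 0.03 ng/ml before theatre who is still above it on day 1.
- Level: met.
- Window: met, because the day-1 sample falls within it.
- Attribution: an assessor may discount a chronic elevation put down to, say, kidney disease. Myocardial injury that preceded theatre is still myocardial injury, so it satisfies the clause. No assessor, written criteria or earlier comparator is named.

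Such a patient can therefore count as an event, although the background's description would not cover an unchanged level.

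**2. Size of one misclassification.** Inputs: 15 per cohort (Trial Summary) and 2.8% (section 1.2).
- Shift in one cohort: 1/15 = 6.7 percentage points.
- Expected events at the cited rate: 15 × 0.028 = 0.42 per cohort, and 30 × 0.028 = 0.84 overall.

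One misclassified patient thus exceeds the number of genuine events expected in the whole study at that rate. The 2.8% comes from a non-cardiac surgery cohort, not a hip-fracture one, so it is only a rough reference.

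**3. Larger effects, hypothetical only.** Let f be the share of patients who were raised before surgery, are tested, are still raised afterwards and are not discounted. The documents give no value for f, so 5% to 40% is purely an assumption. Apparent incidence = f + (1 − f) × 0.028.

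| f (assumed) | Apparent incidence | Events in 30 | Of which already raised (30f) |
|---|---|---|---|
| 0 | 2.8% | 0.84 | 0 |
| 5% | 0.05 + 0.95 × 0.028 = 7.7% | 2.3 | 1.5 |
| 10% | 0.10 + 0.90 × 0.028 = 12.5% | 3.8 | 3.0 |
| 20% | 0.20 + 0.80 × 0.028 = 22.2% | 6.7 | 6.0 |
| 40% | 0.40 + 0.60 × 0.028 = 41.7% | 12.5 | 12.0 |

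If the attribution step removes half of the patients with prior elevation, f halves, so a 10% scenario becomes the 5% row. The table shows the direction of the error and how sensitive the rate is to f. It does not estimate what will happen.

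**4. Sampling error for comparison.** One event in 15 has an exact 95% confidence interval of about 0.2% to 32%. The rate is imprecise however the outcome is defined.

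**The case against.** **The attribution clause and the word incidence imply new injury.** That is a natural reading, and a careful assessor might apply it. The clause still gives no criteria and does not mention timing. It reduces the problem without removing it.

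**The cited European perioperative definitions may supply a baseline requirement.** This cannot be checked from the documents. The bullet sets its own explicit rule, so the reference cannot be assumed to override it.

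**Pre-operative troponins may be captured already.** Section 3.2 does not restrict recording to post-operative samples, so this may be true. Nothing says how such a value would be used, and section 2.10.1 describes follow-up as a review of note entries made after theatre.

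**The outcome is secondary, in a feasibility study.** This stands and limits the importance of the point. The sample size does not depend on the outcome, and step 4 of the working shows that the rate could not carry a definitive design alone. Section 6.1 also relies on the literature.

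Some stronger readings are tempting but unsupported:
- A reader might infer that several false events per cohort are to be expected. For example, if 10% to 30% were raised beforehand, 15 × 0.10 = 1.5 to 15 × 0.30 = 4.5 would follow. That needs an unsourced prevalence, every patient tested, levels still raised after surgery and none discounted.
- A reader might infer that the definition could create or hide a difference between cohorts. No between-cohort test of this outcome is specified.
- A reader might infer that the plan relies on one sample. It does not state the number, although nothing prevents a single value from qualifying.
- A reader might infer that the plan expects cardiac and renal comorbidity. Section 2.11.1 says only that it will be recorded, and section 2.4.2 excludes atrial fibrillation, valvular disease and peripheral vascular disease, which may remove some patients with raised baselines.

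**Conclusion.** The point holds in a limited form. Followed as written, section 2.3.3 allows a troponin already above 0.03 ng/ml before theatre to count as an incident event, which does not match the post-operative rise described in section 1.2. This conclusion rests on the wording of the two sections and on the absence of any baseline comparator in sections 3.1 and 3.2. It would weaken if the cited external definitions required a rise and were meant to govern the bullet, which the documents do not show.

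The size is unknown because no rate of pre-operative elevation is given. The only firm figure is 6.7 percentage points per misclassified patient in a cohort of 15. The point does not affect the primary feasibility endpoint or the planned 30 patients. It matters for how the reported incidence is read and used in planning, and it is worth correcting because the correction is cheap.

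**What to change.** Keep the stated cut-off and attribution clause. Add to the CRF the last routine pre-operative troponin, where one exists, and the assay used. No new blood sample is needed, so section 3.2 is respected, and section 2.10.1 already has the follow-up team viewing electronic blood results.

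Report the patients who meet the criterion in three rows:
- **(a) New:** pre-operative value at or below the cut-off.
- **(b) Already raised:** pre-operative value above the cut-off. List both values, and do not count the patient as new on the cut-off alone.
- **(c) Onset unknown:** no pre-operative value.

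State the number of patients tested as the denominator. For planning the definitive trial, give incidence as a range from (a)/tested to (a + c)/tested, alongside the literature. A single rate that leaves out row (c) should not be used. With routine sampling only, patients who have a baseline value are likely to be a selected group, and dropping the others could bias the rate low. The range does not cover genuinely new injury in row (b), which is why both values are listed there.

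The cost is two CRF fields, a short addition to section 2.3.3, and a range instead of one figure. Row (c) may be large because only routine samples are used, but that would itself be a useful feasibility finding.
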